3.4 Exploratory Endpoints

Exploratory endpoints are not covered in the scope of this analysis plan.

4. Analysis Populations

4.1 Safety Population

The safety population includes all patients who received at least 1 dose of study medication in the study and will be the primary analysis set for the assessment of safety and tolerability in the study.

For the purpose of data summaries, patients will be included in the Safety Population according to the dose level initially received, regardless of any subsequent dose adjustments.

4.2 Full Analysis Set

The FAS is based on the *intention-to-treat* principle and includes all treated patients analyzed in accordance with the intended dose group, regardless of the dose actually received. For Part 2 only, the FAS will be used to assess the sensitivity of the primary efficacy analyses to exclusions from the EFR set.

4.3 Evaluable for Response Set

The EFR set is defined as a subset of the FAS, excluding any patients with major protocol deviations. Deviations that would end to exclusion from the FAS are:

- Patient does not have AML as defined by the 2016 revision to the WHO classification of myeloid neoplasms and acute leukemia (failure of inclusion criteria 3)
- Patient is eligible for induction therapy (failure of inclusion criteria 5)
- Patients who are diagnosed with *de novo* myeloid sarcoma without bone marrow involvement (satisfying exclusion criteria 1)
- Patients who are diagnosed with acute promyelocytic leukemia with the *PML-RARA* (satisfying exclusion criteria 2)
- Patients who received any other standard or investigational treatment for their leukemia within the last 7 days before starting the first dose of study drug, with the exception of leukapheresis and hydroxyurea (satisfying exclusion criteria 3)

The EFR set will be the primary analysis set used for the evaluation of all efficacy objectives.

4.4 PK Analysis Set

The PK population contains all patients who have received one complete dose of ASLAN003 and have at least one measured concentration at a scheduled post-dose time point without any major protocol deviations or events that affect the PK concentrations. Patients in this population will be used for all PK analyses.

All PK data will be analyzed according to treatment received.

This population will comprise all data from patients who receive study treatment as per protocol (e.g. 100 mg QD, 200 mg QD, 100 mg BID or 200 mg BID) and did not violate or deviate from the protocol and planned dosing regimen in ways that would significantly affect the PK analyses (for example skipping doses, or taking reduced doses or taking concomitant medications with the potential to cause a drug-drug interaction) during the PK sampling period. Patients who did deviate from the planned dosing regimen may still provide some data for inclusion in the PK set, if they have at least one usable PK profile. The population, and decisions regarding which profiles are usable, will be defined by the Study Team Physician, Pharmacokineticist and Statistician prior to any analyses being performed.

4.5 Summary of Analysis Populations

A summary of the study outcome variables, and associated analysis sets is provided in Table 1.

Table 1 Summary of Outcome Variables and Analysis Populations

Outcome Variable	Analysis Population (Sensitivity Analysis Population)
Efficacy Data	
OCRR, RFS, CBR, TTR, TTCR, BM blasts	EFR (FAS for Part 2 only)
Demography	FAS
Pharmacokinetics	
PK	PK
Safety	
Exposure	Safety
Adverse Events	Safety
Laboratory measurements	Safety
Vital Signs	Safety
ECG	Safety
Physical Examination	Safety

5. Protocol Deviations

5.1 Major Deviations

Major protocol deviations are defined as those that would lead to exclusion from the EFR set (see Section 4).

The following will be classified as major deviations:

- Patient does not have AML as defined by the 2016 revision to the WHO classification of myeloid neoplasms and acute leukemia (failure of inclusion criteria 3)
- Patient is eligible for induction therapy (failure of inclusion criteria 5)
- Patients who are diagnosed with *de novo* myeloid sarcoma without bone marrow involvement (satisfying exclusion criteria 1)
- Patients who are diagnosed with acute promyelocytic leukemia with the *PML-RARA* (satisfying exclusion criteria 2)
- Patients who received any other standard or investigational treatment for their leukemia within the last 7 days prior to starting the first dose of study drug, with the exception of leukapheresis and hydroxyurea (satisfying exclusion criteria 3)
- Patients taking concurrent therapies for leukemia at any time during the study, with the exception of hydroxyurea during the first 14 days, which is permitted under the protocol.

For each part of the study, these protocol deviations will be listed and will be summarized by treatment group.

In addition to the programmatic determination of the major deviations, monitoring notes or summaries will be reviewed to determine any important post entry deviations that are not identifiable via programming, and to check that those identified via programming are correctly classified. The final classification will be made prior to database lock. For example, details of disallowed concomitant medication use will be reviewed by a physician and may be deemed major.

Note, failure of an inclusion/exclusion criteria will not automatically be classified as a major deviation.

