8.3.3 Evaluable for Response Set

The evaluable for response (EFR) set is defined as a subset of the FAS, excluding any patients with major protocol deviations. Deviations that would lead to exclusion from the FAS are:

- Patients who do not have AML as defined by the 2016 revision to the World Health Organization classification of myeloid neoplasms and acute leukemia (failure of inclusion criteria 3 in Section 4.1.

- Patients eligible for induction therapy (failure of inclusion criteria 5 in Section 4.1)
- Patients who are diagnosed with *de novo* myeloid sarcoma without bone marrow involvement (exclusion criteria 1 in Section 4.2)
- Patients who are diagnosed with acute promyelocytic leukemia with the *PML-RARA* (exclusion criteria 2 in Section 4.2)
- Patients who received any other standard or investigational treatment for their leukemia within 7 days before starting the first dose of study drug, with the exception of leukapheresis and hydroxyurea (exclusion criteria 3 in Section 4.2)

The EFR will be the primary analysis set used for the evaluation of all efficacy objectives.

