Other deviations may occur during the trial, which are considered minor and not believed to have any significant impact on the interpretation of the study results. All of these deviations will be recorded by the study monitors but will not be listed or summarized as part of the clinical study report (CSR).

Examples of minor deviations include:

- Visits outside of protocol visit windows
- Incomplete assessments
- Use of concomitant medication related to safety

This list is not exhaustive and other minor deviations may occur.

6. General Statistical Considerations

All statistical analyses will be performed by or under the direct auspices of ASLAN Pharmaceuticals, using SAS® version 9.3 or higher.

Unless specified otherwise, data from Part 1 and Part 2 will be presented separately in the Tables, Figures and Listings.

The following descriptive statistics will be presented in summary tables:

- Continuous variables: number (non-missing cases), mean, median, standard deviation (SD), minimum, and maximum
- Categorical variables: will be summarised by treatment group using frequency tables (frequencies and percentages). Percentages are routinely based on the total category count excluding the missing category if not otherwise mentioned. Missing category with zero count will not be presented
- Time to event endpoints: Will be summarised based on Kaplan Meier estimates

In general, the number of decimal places displayed for each statistic will be determined as follows with a maximum of three decimal places with the exception of the summary of PK results described separately below:

- Mean and median: one more than the number of decimal places allotted in the raw data received from data management
- SD: two more than the number of decimal places allotted in the raw data
- Minimum and maximum: equal to the number of decimal places allotted in the raw data
- Confidence Intervals (CIs) will be presented using the number of decimal places plus one as the parameters (e.g. mean) as appropriate
- P-values greater than or equal to 0.0001, in general, will be presented to four decimal places. P-values less than 0.0001 will be presented as "<0.0001 and p-value greater than >0.9999 will be presented as 1.0000
- Percentages will be reported to one decimal place

Specific rules for pharmacokinetics:

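### SAP 5.1 adds a sixth, post-dose exclusion from the EFR set that Protocol 8.3.3 and SAP 4.3 do not list, so the primary OCRR has two possible denominators; the FAS check for Part 1 is also stated inconsistently

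*SAP*

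**What the plan says.** **EFR set.** SAP 4.3 defines it as the FAS "excluding any patients with major protocol deviations", then lists five deviations: not AML by the WHO 2016 classification, eligible for induction therapy, myeloid sarcoma without marrow involvement, PML-RARA disease, and other leukaemia treatment in the 7 days before first dose. Protocol 8.3.3 has the same five. SAP 4.3 adds: "The EFR set will be the primary analysis set used for the evaluation of all efficacy objectives".

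**Major deviations.** SAP 5.1 states: "Major protocol deviations are defined as those that would lead to exclusion from the EFR set". It points back to Section 4, repeats the five items and adds a sixth: "Patients taking concurrent therapies for leukemia at any time during the study, with the exception of hydroxyurea during the first 14 days". It also provides for a check before database lock, partly "to check that those identified via programming are correctly classified", and gives as an example that "details of disallowed concomitant medication use will be reviewed by a physician and may be deemed major".

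**Hydroxyurea.** Protocol 5.9.2 allows it in the first two weeks for patients with a high peripheral blast count. It separately allows it for suspected or confirmed differentiation syndrome and states no day limit for that use.

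**OCRR rule.** SAP 3.1.1 disregards response data collected after subsequent AML therapy begins, and counts patients with no evaluable post-treatment assessment as non-responders.

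**FAS sensitivity analysis.** SAP 3.1.1 to 3.1.4 plan it in all study parts for OCRR, relapse-free survival, clinical benefit rate and marrow blasts. Protocol 8.3.2 sets no limit by part. SAP 9.1 repeats its tables, including the FAS OCRR table (14.2.1.2), for both parts by default. SAP 4.2 and Table 1 restrict the analysis to Part 2.

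**The concern.** OCRR in the EFR set is the primary endpoint of Part 2 and a co-primary endpoint of Part 1. In a single-arm estimation study the denominator is part of the result. An analyst who applies SAP 4.3 and one who applies SAP 5.1 can both follow the text and report different rates.

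The sixth item differs in kind from the other five. They are fixed by first dose. The sixth depends on what happens afterwards, and its wording does not distinguish therapy given before a documented response from therapy given after it. It also departs from SAP 3.1.1, which handles later AML therapy by cutting off the data and keeps unevaluable patients in the denominator.

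The 14-day exception is narrower than the protocol's permission, so literal use could remove a patient who was treated within the protocol. The pre-lock check might catch this, but no written rule says that it must.

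The FAS analysis is the check on EFR exclusions. It is stated inconsistently for Part 1, where the cohorts have only six patients and the results inform dose selection.

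**Working it through.** The documents give no target rate, power or decision threshold, so there is no planned figure to reproduce. The check is a comparison of text, followed by an illustration of size.

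**Step 1. The three EFR lists**

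| Exclusion | Protocol 8.3.3 | SAP 4.3 | SAP 5.1 | When settled |
|---|---|---|---|---|
| Not AML (WHO 2016) | yes | yes | yes | by first dose |
| Eligible for induction therapy | yes | yes | yes | by first dose |
| Myeloid sarcoma without marrow involvement | yes | yes | yes | by first dose |
| PML-RARA disease | yes | yes | yes | by first dose |
| Other leukaemia treatment within 7 days before dosing | yes | yes | yes | by first dose |
| Concurrent leukaemia therapy (hydroxyurea exempt for 14 days) | no | no | yes | after first dose |

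The opening of SAP 4.3 could be read as importing whatever SAP 5.1 calls major. But the list that follows has five items and is not introduced as examples, and SAP 5.1 refers back to Section 4. The cross-reference is circular and does not settle the matter.

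Both five-item lists are also introduced under the wrong name. Protocol 8.3.3 reads "Deviations that would lead to exclusion from the FAS are", and SAP 4.3 likewise names the FAS where the EFR is evidently meant.

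**Step 2. The FAS statements**

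| Place | Part 1 | Part 2 |
|---|---|---|
| Protocol 8.3.2 | no limit by part | no limit by part |
| SAP 3.1.1 to 3.1.4 | yes | yes |
| SAP 9.1 (tables 14.2.1.2, 14.2.2.2, 14.2.3.2) | yes, by default | yes |
| SAP 4.2 and Table 1 | no | yes |

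**Step 3. Illustrative size, Part 2**

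Inputs from the documents: n = 20 (SAP 6.1.2) and a two-sided 80% Clopper-Pearson interval (SAP 7.1). Responder and exclusion counts are assumptions, because the documents give none.

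For x responders of n, the lower limit is the 10th percentile of Beta(x, n − x + 1) and the upper limit is the 90th percentile of Beta(x + 1, n − x). At 4/20 the two binomial tail probabilities at these limits are 0.100 and 0.100, as they should be.

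| Removed by the sixth item | OCRR | 80% CI | Shift in points |
|---|---|---|---|
| nobody | 4/20 = 20.0% | 9.0 to 36.1 | – |
| 1 non-responder | 4/19 = 21.1% | 9.5 to 37.8 | +1.1 |
| 2 non-responders | 4/18 = 22.2% | 10.1 to 39.6 | +2.2 |
| 3 non-responders | 4/17 = 23.5% | 10.7 to 41.6 | +3.5 |
| 1 responder | 3/19 = 15.8% | 5.9 to 31.9 | −4.2 |
| 2 responders | 2/18 = 11.1% | 3.0 to 26.9 | −8.9 |

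The 4/20 interval is 36.1 − 9.0 = 27.1 points wide.

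**Step 4. Illustrative size, Part 1 cohort of 6 (no interval planned)**

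With 1 responder, 1/6 = 16.7% becomes 1/5 = 20.0% if a non-responder is removed, or 0/5 = 0% if the responder is. With 2 responders, 2/6 = 33.3% becomes 2/5 = 40.0% or 1/5 = 20.0%.

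**The case against.** **The effect is small.** There is no formal test or decision threshold, dose selection rests on the data as a whole, and the Part 2 FAS OCRR is planned under every passage. This stands, and it limits the severity.

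**Part 1 is not without a check.** A reader might infer from SAP 4.2 and Table 1 that no FAS OCRR will be produced for Part 1. The documents do not support that: SAP 9.1 plans the table for both parts by default, and SAP 9.2 lists response patient by patient on the FAS, so either denominator can be rebuilt. What remains is a contradiction, since SAP 4.2 could count as the stated exception to the default.

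**Late hydroxyurea may not be caught.** Used for differentiation syndrome, it is arguably treatment of an adverse event and not therapy for leukaemia, and the pre-lock check could reclassify it. But SAP 5.1 exempts hydroxyurea for 14 days only, which implies that later use counts. A reader might also infer a second, competing class from the minor-deviation example "Use of concomitant medication related to safety" in SAP 5.2. That does not fit naturally, because use that the protocol permits is not a deviation at all.

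**Responders are unlikely to be removed.** A reader might infer that a responder who starts other therapy after stopping study drug is excluded. SAP 7.10 separates concomitant from post-treatment medication, and SAP 9.2 lists subsequent antileukaemic treatment separately, so concurrent most likely means during study drug. The downward scenarios then need a responder who takes other leukaemia therapy while on study drug, or late hydroxyurea read literally.

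**Six items everywhere would also be consistent.** This is true, and Protocol 5.9.2 does show concern that hydroxyurea could affect the efficacy readout. But that choice would keep a post-dose exclusion from the primary set, whereas the data cut-off in SAP 3.1.1 can deal with later therapy without removing the patient.

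**Conclusion.** The concern holds as a conflict in the definition of the primary analysis set. Protocol 8.3.3 and SAP 4.3 give five baseline exclusions; SAP 5.1 gives six, the last of them post-dose. Its hydroxyurea exception is narrower than Protocol 5.9.2, and only a case-by-case check before lock stands between the literal rule and the exclusion of a protocol-compliant patient. The Part 1 FAS analysis is contradicted within the SAP.

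The size is modest and rests on assumed counts. From 4/20, removing one to three non-responders raises OCRR by 1.1 to 3.5 points, against an interval about 27 points wide. One removed responder lowers it by 4.2 points. In a cohort of six, one exclusion can matter more. A reader might infer that the sixth item inflates OCRR; the documents do not support a direction, because that depends on who is removed, and they give no rate of such therapy. It should be fixed before database lock, but it does not threaten the study.

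**What to change.** 1. Use the same five baseline criteria for EFR exclusion in Protocol 8.3.3, SAP 4.3 and SAP 5.1. State that no post-dose event, including one found at the pre-lock review, removes a patient from the EFR set.
2. List on-study leukaemia therapy as an important deviation in SAP 5.2 and keep the patient in the OCRR denominator.
3. Extend the data cut-off in SAP 3.1.1, now written for subsequent AML therapy, to prohibited anti-leukaemia therapy taken during study drug. State that protocol-permitted hydroxyurea does not trigger it.
4. Reconcile the hydroxyurea text of SAP 5.1 with Protocol 5.9.2.
5. Amend SAP 4.2 and Table 1 to match SAP 3.1.1 to 3.1.4 and 9.1, so that FAS OCRR is reported for both parts.
6. In Protocol 8.3.3 and SAP 4.3, replace FAS with EFR in the sentence that introduces the exclusions.

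The cost is wording changes and at most one extra Part 1 summary. No new data or patients are needed. The reported OCRR may move slightly in either direction.

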5.2 Other Important Deviations

In addition to the programmatic determination of the major deviations as described in Section 5.1, the following *important deviations* will be programmatically derived and listed and summarized:

- Failure of any remaining inclusion/exclusion criteria

Errors in dispensing will be summarized and listed as *important deviations*. These include:

- Patients who receive no study treatment whatsoever for a period of more than one week due to errors in dispensing of medication. Note, this is not due to tolerability issues where patients may stop taking drug.
- Patients who at some point receive the incorrect dose of ASLAN003.

In addition, other non-programmable important deviations will be collected on the case report form (CRF), listed and summarized including, but not limited to:

- Patients of child-bearing potential not practicing acceptable methods of birth control from the time they enter the screening period until 3 months after the last cycle of treatment.
- Patients breast feeding at any point between the time they enter the screening period until 3 months after the last cycle of treatment.

Compliance will be assessed by Study Team review of protocol procedures with specific attention paid to missed dosing due to reasons other than AEs. (E.g, patients receiving <75% of intended doses) and will not be assessed programmatically. Any compliance issues considered likely to impact on the interpretation of safety or efficacy will be added to the deviation CRF page.

Finally, monitoring notes or summaries will be reviewed to determine any important post entry deviations that are not identifiable via programming, and to check that those identified via programming are correctly classified. The final classification will be made prior to database lock. For example, details of disallowed concomitant medication use will be reviewed by a physician and if deemed important, may also be included in the listing of important deviations.

All patients who failed any inclusion/exclusion criteria will be listed along with details of the failed criteria. This information will also be summarized in terms of the number (%) of patient failing any of the inclusion/exclusion criteria and will be based on the FAS. Note, failure of an inclusion/exclusion criteria will not automatically be classified as a major deviation.

Other deviations may occur during the trial, which are considered minor and not believed to have any significant impact on the interpretation of the study results. All of these deviations will be recorded by the study monitors but will not be listed or summarized as part of the clinical study report (CSR).

Examples of minor deviations include:

- Visits outside of protocol visit windows
- Incomplete assessments
- Use of concomitant medication related to safety

This list is not exhaustive and other minor deviations may occur.

6. General Statistical Considerations

All statistical analyses will be performed by or under the direct auspices of ASLAN Pharmaceuticals, using SAS® version 9.3 or higher.

Unless specified otherwise, data from Part 1 and Part 2 will be presented separately in the Tables, Figures and Listings.

The following descriptive statistics will be presented in summary tables:

- Continuous variables: number (non-missing cases), mean, median, standard deviation (SD), minimum, and maximum
- Categorical variables: will be summarised by treatment group using frequency tables (frequencies and percentages). Percentages are routinely based on the total category count excluding the missing category if not otherwise mentioned. Missing category with zero count will not be presented
- Time to event endpoints: Will be summarised based on Kaplan Meier estimates

In general, the number of decimal places displayed for each statistic will be determined as follows with a maximum of three decimal places with the exception of the summary of PK results described separately below:

- Mean and median: one more than the number of decimal places allotted in the raw data received from data management
- SD: two more than the number of decimal places allotted in the raw data
- Minimum and maximum: equal to the number of decimal places allotted in the raw data
- Confidence Intervals (CIs) will be presented using the number of decimal places plus one as the parameters (e.g. mean) as appropriate
- P-values greater than or equal to 0.0001, in general, will be presented to four decimal places. P-values less than 0.0001 will be presented as "<0.0001 and p-value greater than >0.9999 will be presented as 1.0000
- Percentages will be reported to one decimal place

Specific rules for pharmacokinetics:

Plasma concentrations of ASLAN003 and LAS186558 will be presented descriptively by study day and nominal time point for the PK analysis set including number of subjects (N), number of observations (n), mean, SD, coefficient of variation (CV%) median, minimum, and maximum. The below limit of quantification (BLQ) PK concentration values will be set to zero prior to computing descriptive statistics of PK concentrations. Missing concentrations will be omitted from the calculation of descriptive statistics.

Individual plasma and mean concentration-time plots will be provided using a linear and semi-logarithmic scale.

Descriptive statistics for PK parameters (see Section 7.11 for calculations) will be summarized by study day (N, n, arithmetic mean, SD of the arithmetic mean, CV%, median, minimum, maximum geometric mean [GeoMean], and geometric coefficient of variation [GeoCV%]). For t_{max} , only n, minimum, median, and maximum will be reported. For calculation and presentation of PK parameter descriptive statistics, values as presented in the data listings will be used as the source data. Minimum, maximum, mean, GeoMean, and median will be presented to the same significant figure precision as listed data. Standard deviation will be presented to 1 significant figure more than the precision of the data listed. The CV% and GeoCV% will always be reported to 1 decimal place. Derived parameters will be reported to 3 significant

figures, except for parameters that are taken directly from concentration data which will be reported using similar precision to those from which they were derived or elapsed sampling times which will be reported as 2 decimal places.

Scatter plots of individual subject and geometric mean dose-normalized AUC_{tau} (or AUC_{last}), $AUC_{tau ss}$ (or $AUC_{last ss}$), C_{max} and $C_{max ss}$ values versus dose will be presented.

